#### 7.4.3. Hypersensitivity reaction to trimethoprim-sulfamethoxazole

If the patient develops a hypersensitivity reaction to TMP/SMZ manifested by a suspicious skin rash or other acute allergic symptoms, the medication will be discontinued promptly. The subject will continue to receive remaining IVIG infusions and followed as per protocol.

#### 7.4.4. Aseptic meningitis syndrome (AMS)

AMS may occur infrequently with IVIG treatment. Discontinuation of IVIG treatment has resulted in remission of AMS within several days without sequelae. Administration of corticosteroids may also be helpful, the decision made upon consultation with neurology or infectious diseases specialists. The syndrome usually begins within several hours to two days following IVIG treatment and is characterized by the following symptoms and signs: severe headache, nuchal rigidity, drowsiness, fever, photophobia, painful eye movements, nausea and vomiting. Cerebrospinal fluid (CSF) studies are frequently positive with pleocytosis up to several thousand cells per cu mm, predominantly from the granulocytic series, and with elevated protein levels up to several hundred mg/dL, but negative culture results. Subjects enrolled in this study who exhibit any of these symptoms or signs will have a thorough neurological examination performed including

CSF studies, to rule out other causes of meningitis. Because AMS may occur more frequently in association with high doses (2 g/kg) and/or rapid infusion of IVIG, the risk of AMS will be lowered in this study by using 1 g/kg doses of IVIG and using slow infusion rates. The occurrence of AMS will be an indication to discontinue any further IVIG infusions in the subject.

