# 6.1.5.b. Side effects of IVIG

The second set of potential risks derive from reported side effects of IVIG which include headache, irritability, flu-like symptoms, fever, nausea, fluid overload, allergic reactions, local infusion site reactions, viral contamination of the product, interference with live vaccines, aseptic meningitis, renal dysfunction, thrombotic events, hypotension and hypoglycemia. All of these side effects are uncommon or not serious in infants and young children (45-46). Despite these potential adverse events, this clinical trial is justified by the devastating nature of BA on the well-being of affected children and on the progression to end-stage liver disease in most patients with the prospects for improved care of future patients with BA if IVIG is found to be beneficial. In this context, IVIG treatment may result in reduced hepatic inflammation, improved bile flow, allow for better

growth, and increase long-term survival with the native liver. To minimize potential adverse events to subjects, it is recommended that the IVIG be diluted to a 5% solution when administered into a peripheral vein if this is acceptable by the local institutional policy. In addition, the clinical site staff will monitor all subjects closely during each IVIG infusion for side effects, and promptly adhere to their institutional action plan and that outlined in the Data Safety Monitoring Plan (DSMP) if side effects are identified (see Section 7.4).

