#### 7.4.2. Irritability

The development of severe irritability in the subject without an obvious cause will be considered a moderate AE, defined as the presence of inconsolable, persistent crying without an apparent cause, which requires evaluation and confirmation by the primary care provider or a visit to an emergency department if the patient is being followed as an outpatient, or evaluation by the clinical inpatient or outpatient team if the patient is in hospital receiving IVIG infusion at the time of the event. If the severe irritability develops during an IVIG infusion, the infusion will be slowed down or stopped. Following evaluation for irritability and if no obvious cause is identified, the subject will be treated symptomatically and will not receive additional doses of IVIG. Consideration for a lumbar puncture and evaluation for the rare aseptic meningitis syndrome (see 7.4.4) that has been reported with IVIG therapy will be based on the clinical discretion of the treating physician. The irritability may also be a manifestation of headaches that occur in 20-30% of adults who receive comparable doses of IVIG.

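### Section 7.4.4 makes CSF studies mandatory for any single listed sign, such as an isolated fever, without requiring a recent infusion or suspected meningitis

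*Protocol*

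**What the plan says.** Section 7.4.4 describes AMS by these features: "severe headache, nuchal rigidity, drowsiness, fever, photophobia, painful eye movements, nausea and vomiting". It gives the usual timing as a description: "The syndrome usually begins within several hours to two days following IVIG treatment". The operative rule is "Subjects enrolled in this study who exhibit any of these symptoms or signs will have a thorough neurological examination performed including". The sentence then names the invasive part and its purpose: "CSF studies, to rule out other causes of meningitis". If AMS occurs, the infant receives no further IVIG.

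Section 7.4.2 deals with severe irritability that has no obvious cause. It refers to 7.4.4 and covers "Consideration for a lumbar puncture and evaluation for the rare aseptic meningitis syndrome". The decision, it says, "will be based on the clinical discretion of the treating physician". It adds: "The irritability may also be a manifestation of headaches".

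Section 6.1.5.b lists reported IVIG side effects, including "headache, irritability, flu-like symptoms, fever, nausea, fluid overload, allergic reactions". Aseptic meningitis appears later in that list as a separate item.

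**The concern.** The rule in 7.4.4 joins a low trigger (any one sign on the list) to a mandatory invasive step. It sets no time limit after an infusion, does not ask whether meningitis is suspected, and gives the physician no room to attribute the sign to something else. Section 4.14 adds that every study procedure described in the protocol is mandatory.

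A physician who sees an infant with a fever and an evident other cause must then either order CSF studies or depart from the protocol. What is at stake is the burden and risk to the infant and avoidable protocol deviations.

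**Working it through.** The protocol gives no figure to reproduce here, so the check compares sections.

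**1. What triggers the work-up.** In 7.4.4 the trigger is any listed item and the instruction is mandatory. Timing after IVIG appears in a separate descriptive sentence. The reference to other causes of meningitis states why the work-up is done, and is not a condition for doing it.

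**2. When the rule applies.** Section 7.4 says monitoring for these adverse events takes place before the first dose, at hospital discharge and at each scheduled follow-up visit. Table 3 runs those visits to day 360. Nothing in 7.4.4 confines the rule to the days after an infusion. For an infant who gets all three doses, starting on day 3, and is followed to day 360:
- usual AMS onset period: 3 infusions × 2 days = 6 days
- follow-up from the first dose: 360 − 3 = 357 days
- share: 6 / 357 = 1.7%

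The onset period is described as usual, not absolute, so this shows only how much wider the written rule is than the syndrome it targets.

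**3. How the protocol regards fever elsewhere.**
- 6.1.5.b: a reported IVIG side effect, listed apart from aseptic meningitis.
- 7.2.1: an event that progression of biliary atresia can itself produce.
- 7.4.8: a manifestation of hypersensitivity to IVIG, managed by stopping the infusion and treating, with no CSF step.
- 4.6: a possible manifestation of a reaction to trimethoprim-sulfamethoxazole.
- 7.4.11: part of the picture of transfusion-related acute lung injury.

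An infant with fever, rash and urticaria during an infusion is fully managed under 7.4.8. Taken literally, 7.4.4 would require CSF studies in that infant as well. Limiting the rule to signs after an infusion would therefore help but would not be enough.

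**4. Comparison with 7.4.2.** The trigger there is unexplained severe irritability, the syndrome in view is the same AMS, and the decision on lumbar puncture rests with the treating physician. Irritability is not on the 7.4.4 list. A site can obey both sections, so they do not conflict. The comparison shows only that the protocol already accepts clinical judgment on lumbar puncture for suspected AMS.

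**The case against.** **Context.** The sentence stands under an AMS heading in a section on IVIG side effects, follows a description of onset after treatment, and speaks of other causes of meningitis. The authors probably meant suspected AMS after an infusion. That is a fair reading of intent, but the rule does not say it, and sites work from the rule.

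**Deliberate caution.** A low threshold could be defended in young post-operative infants given an agent not previously used in this disease. Infants cannot report headache, so non-specific signs may be all there is to see. The documents do not show that a low threshold is clinically wrong. The revised rule still examines every infant with a listed sign after an infusion and permits CSF studies whenever suspicion exists.

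**Nausea and vomiting as one item.** The list can be read that way, and vomiting alone might then not be a trigger. Fever and drowsiness remain single triggers on either reading.

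**Ascertainment.** Aseptic meningitis is named in safety outcome 3c (4.3.1). Moving from a uniform rule to judgment across 16 centers could leave a mild case without CSF confirmation. This objection stands, and the fix has to allow for it.

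**Stronger inferences that the documents do not support.**
- A reader might conclude that 7.4.2 and 7.4.4 contradict each other. They have different triggers and do not.
- A reader might want a forecast of unneeded lumbar punctures. The protocol gives no rate for the listed signs in infants, so any count would rest on assumed rates alone.
- A reader might infer that families were not warned of lumbar puncture. Section 6.1.5.b names aseptic meningitis and points to 7.4, and the consent form was not available for this review.

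**Conclusion.** The point holds as a matter of safety wording. As written, 7.4.4 mandates CSF studies for one non-specific sign at any time in follow-up, which is broader than its own description of AMS and than the protocol's treatment of fever elsewhere. The conclusion rests on the plain wording of 7.4.4. The statement in 4.14 reinforces it but is not essential.

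The size is minor to moderate. The number of infants affected cannot be estimated from the documents. Sample size and power do not change.

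**What to change.** Replace the sentence in 7.4.4 with wording such as:

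*A subject who develops one or more of these findings after an IVIG infusion (usually within two days) will have a full neurological examination. CSF studies will be performed when the treating physician suspects AMS or another meningitis and the findings are not explained by another cause.*

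Record for each AMS case whether the diagnosis was CSF-confirmed or clinical, so that the aseptic meningitis component of outcome 3c can be reported both ways.

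**Cost.** One sentence in an amendment and one item on the adverse event form. The downside is that a mild case may rest on clinical grounds only. One infant classified differently changes a percentage by at most 1/29 = 3.4 points, or 1/23 = 4.3 points at the protocol's lower figure for treated subjects. The change in 3c is smaller still if that infant already counts for another expected event. Visits and sample size stay as they are.

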# 7.4.5. Renal Dysfunction

Development of acute renal failure may occur during IVIG administration in patients who are volume depleted at the time of IVIG administration or in patients with underlying renal dysfunction. For this reason an exclusion criteria for this trial is the presence of underlying renal dysfunction or significant congenital renal malformations. Renal dysfunction and acute renal failure occur more commonly in patients receiving IVIG products containing sucrose; the preparation used in this clinical trial does not contain sucrose. To prevent development of acute renal failure, we will assure that patients are not volume depleted prior to the initiation of the infusion of IVIG. Periodic monitoring of renal function and urine output will be performed during outpatient follow up. Renal function (measurement of blood urea nitrogen (BUN)/serum creatinine) will be measured prior to the initial infusion of IVIG and before each subsequent dose. If renal function worsens (doubling of baseline serum creatinine that exceeds the upper limit of normal) in a subject during this trial, IVIG infusions will be discontinued.

# 7.4.6. Fluid volume overload

Because of the fluid volume administered with each IVIG infusion in this study (20 ml per kg body weight of a 5% Gammunex-C solution over 4-8 hours for each infusion), individuals with expanded fluid volume, or where fluid volume may be a concern, will not be enrolled in this study. On the day of doses #2 and #3, the physical exam must be completed by a physician prior to the infusion to rule out signs of fluid overload or congestive heart failure. IV fluids will be reduced by 20 ml per kg per day for the day that dose #1 is administered, and if IV fluids are being administered for the days that doses #2 and #3 are given. If fluid volume problems develop during an IVIG infusion, the infusion will be stopped and appropriate steps will be taken to reduce fluid intake and consideration of use of intravenous diuretic medications (e.g. furosemide I mg/kg IV). If fluid volume status has improved at the time of the subsequent IVIG dose, the dose may be given.

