IVIG will be initiated on day 3-5 after HPE surgery (HPE is day 0) at a dose of 1 gm/kg body weight by slow intravenous infusion over at least 4-8 hours, or according to local clinical guidelines for rate and time of infusion. The same dose (1 gm/kg) and duration of infusion will be repeated on day 30 and on day 60 after HPE. Ideally the first dose will be administered on day 3 after HPE, however the first dose may be administered on day 4 or 5 after HPE if there is a clinical situation that precludes start of the study medication on day 3. Dose #1 must be given while the subject is still hospitalized. Dose #2 and #3 may be given as outpatient infusions at the study site if the subject has been discharged from the hospital, as expected. The dose will be based on the weight of the subject on the day of the infusion. If the subject has an intercurrent illness or infection that would preclude giving the 2nd or 3rd IVIG dose at the specified times, the subject will be stabilized or treated for this illness and then the IVIG will be given if the investigator believes it will be tolerated. Since there is a 10 day window for administering doses #2 and #3 of IVIG, we anticipate that all doses will be able to be given during this window. If dose #2 is missed for reasons other than an IVIG related adverse event, dose #3 may still be given. Standard precautions will be taken for administering IVIG, including administering IVIG in a controlled setting by experienced nursing staff, and with the immediate availability of intravenous diphenhydramine, intravenous or subcutaneous epinephrine, and oral or rectal acetaminophen. Local site standard protocol for administration of IVIG will be followed, which may include premedication with acetaminophen or diphenhydramine.

A single dosage level of 1 gm/kg of IVIG was chosen for this study (rather than a range of escalating doses) because 1) this dose is effective and commonly used to treat other autoimmune or immune-mediated diseases in children and adults, 2) this dose can be administered intravenously over 6-8 hours during an outpatient research visit, and 3) this dose is usually not associated with significant side effects in children. To attempt to study several escalating doses in this study would imply that there was a therapeutic target for serum IgG that we would be trying to achieve and that the proper dose could be determined based on PK/PD studies. However, there is no target serum level of IgG that is

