known to be effective for BA or for other diseases and, thus, PK/PD studies would be difficult to interpret. Therefore, we chose to use a high dose of IVIG that is effective in other immune-mediated diseases in children and adults and that should be well tolerated by the infants and their families.

Route of Administration: Dose #1 of IVIG will be administered through peripheral IV, central venous catheter or PICC line, whichever is in place for clinical indications on days 3-5 following HPE. It is mandatory that dose #1 be administered during the inpatient post-operative period following HPE. It is anticipated that doses #2 and #3 of IVIG will be administered in the outpatient setting, although these doses could be administered in the inpatient setting if the subject had been admitted to hospital for a clinically indicated reason. If no IV is in place at the prescribed time for doses #1, #2, or #3 of IVIG, then a peripheral IV will be started for the study drug administration and removed after administration of the IVIG. If the family does not allow placement of a peripheral IV for a dose of IVIG, then that dose of IVIG will not be given but the subject will remain in the study and follow the rest of the study protocol, including attempts at administering subsequent IVIG doses.

IVIG Infusion	Day of dosing following HPE*	IVIG dose**
#1	Day 3 (up to day 5)	1 gm/kg body weight
#2	Day 30	1 gm/kg body weight
#3	Day 60	1 gm/kg body weight

Table 2. Schedule and dosing of IVIG following HPE in infants with biliary atr	esia.
--	-------

\*See 4.4.4 Dose and Timing

\*\*Initial dose will be based on subject's weight at time of HPE. Subsequent doses will be adjusted based on subject's weight measured at 30 and 60 days after HPE. HPE = hepatic portoenterostomy; IVIG = intravenous immunoglobulin

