### 4.11. Preparation and administration of study medication

#### 4.11.1. Preparation, packaging, and labeling

IVIG that will be used in this study will be Gamunex-C® (immune globulin [human],10%), from a single lot. The IVIG will be shipped periodically to the research pharmacy at each clinical site and stored under standard conditions until used for this study. The IVIG will be labeled "For Investigational Use Only".

Other study medications (ursodeoxycholic acid and TMP-SMZ will be dispensed by the clinical site research pharmacist during this trial. At each follow-up visit, dosing will be adjusted according to the infant's weight. Changes in infant's weight and dosage will be captured in the database and will be communicated to the family by the research coordinator.

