## 7.4.1. Elevation in Blood Pressure related to Increased Fluid Volume

Although unlikely, hypertension could develop due to the fluid volume administered with each IVIG infusion in this study (20 ml per kg body weight over 6-8 hours for each infusion). Vital signs will be continually monitored during the IVIG infusions per institutional protocol. If hypertension develops (systolic BP ≥112 mmHg) during an IVIG infusion, the infusion rate will be reduced or stopped and BP will be measured again in 30 minutes. If BP remains elevated, intravenous furosemide (1 mg/kg/dose) will be an option based on the clinical judgment of the treating physician if fluid volume is considered the likely cause of the hypertension. Alternatively, if the patient is asymptomatic, BP can be re-measured for 30 minutes without treatment. Blood pressure will continue to be monitored each 15 minutes until resolution of the hypertension. If the IVIG infusion must be stopped completely, the subject will not receive further doses of IVIG.

Additional treatment options for the hypertension include:

- a. Treatment choices for hypertension with BP ≥112 mmHg without symptoms
  - Hydrochlorothiazide: 2 mg/kg/day given once or twice a day, or
  - Amlodipine: 0.2-0.4 mg/kg/day given once or twice a day, or
  - Captopril: 0.3-1 mg/kg/day given twice a day
  - Other site-specific treatment choice
- b. Treatment choices for hypertension with BP ≥112 mmHg with symptoms
  - Nifedipine 0.25-0.5 mg/kg/ sublingual
  - Labetolol: 1-3 mg/kg/hour IV
  - Other site-specific treatment of choice

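### Section 7.4.6 cuts IV fluids by a fixed 20 mL/kg on IVIG days, which matches the infused volume only at 5%; with undiluted 10% product, which the protocol permits, the cut can exceed that volume by up to 10 mL/kg

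*Protocol*

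**What the plan says.** Two safety sections give the volume of each infusion as one number. Section 7.4.1 puts it at "20 ml per kg body weight over 6-8 hours for each infusion", without naming a concentration. Section 7.4.6 puts it at "20 ml per kg body weight of a 5% Gammunex-C solution over 4-8 hours for each infusion". Section 7.4.6 then sets the bedside rule: "IV fluids will be reduced by 20 ml per kg per day for the day that dose #1 is administered". The rule extends to doses #2 and #3 only if IV fluids are being given on those days.

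Other sections leave the concentration open:

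- Section 4.11.1 describes the supplied product as "immune globulin [human],10%), from a single lot".
- Section 6.1.5.b says it is "recommended that the IVIG be diluted to a 5% solution when administered into a peripheral vein if this is acceptable" under local institutional policy. That is a recommendation, it covers peripheral veins only, and it yields to local policy.
- Section 4.4.4 says "Dose #1 of IVIG will be administered through peripheral IV, central venous catheter or PICC line", according to what is already in place. It also has sites follow their own standard protocol for giving IVIG.

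No section links the size of the fluid cut to the concentration infused.

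**The concern.** The 20 mL/kg cut equals the 5% infusion volume stated in the same section, so its evident purpose is to offset the volume that the drug adds. It does so only if the drug is given at 5%. The protocol permits the 10% product undiluted, certainly through a central or PICC line and also through a peripheral vein where local policy does not accept dilution. A site that follows 7.4.6 literally would then take away more IV fluid than the infusion supplies.

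The infants concerned are 3-5 days past a portoenterostomy. Section 7.4.5 names volume depletion at the time of IVIG administration as a setting for acute renal failure, so an error towards too little fluid is not automatically the safe one. What is at stake is one day's fluid order. No outcome, estimate or sample size depends on it.

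**Working it through.** **Inputs from the protocol**

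- Dose: 1 g/kg per infusion (4.4.4).
- Concentration supplied: 10%, that is 0.10 g/mL (4.11.1).
- Concentration assumed in 7.4.6: 5%, that is 0.05 g/mL.
- Ordered cut in IV fluids: 20 mL/kg on the day (7.4.6).
- Minimum weight at enrolment: 2,000 g (4.2.1).

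**Input not in the protocol**

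- F, the IV fluid ordered for that day in mL/kg before the cut. It is treated as an assumption and varied.

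**Step 1: reproduce the stated volume.** Volume per kg = dose / concentration. At 5%: 1 / 0.05 = 20 mL/kg. This is the figure in 7.4.6, so that figure is correct for the solution it names.

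**Step 2: the other permitted concentration.** At 10%: 1 / 0.10 = 10 mL/kg. The single volume in 7.4.1 and 7.4.6 is therefore not true of every permitted infusion.

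**Step 3: infused volume less the full cut.**

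- At 5%: 20 - 20 = 0.
- At 10%: 10 - 20 = -10 mL/kg. At 2.0 kg this is 10 x 2.0 = 20 mL.

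**Step 4: allow for the fluid actually running.** The cut cannot remove more than was ordered, so the amount removed is min(F, 20). With V the IVIG volume in mL/kg, the excess of the cut over the infused volume is max(0, min(F, 20) - V).

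| F (mL/kg, assumed) | Excess at 10% (V = 10) | Excess at 5% (V = 20) |
|---|---|---|
| 10 or less | 0 | 0 |
| 15 | min(15, 20) - 10 = 5 | 0 |
| 20 or more | 20 - 10 = 10 | 0 |

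So 10 mL/kg is an upper bound. It needs a full undiluted dose and at least 20 mL/kg of IV fluid ordered that day. These figures leave out enteral feeds, which would reduce any gap.

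**The case against.** The strongest reply is that 7.4.6 concerns fluid overload, names the 5% solution and sets a deliberately cautious flat rule. On that view, preferring an exact match is a clinical preference, and the undiluted case is inferred: no section directs an undiluted infusion, and the protocol does not say how often one would occur. Protection also exists already. Dose #1 must be given in hospital, vital signs are monitored during infusions (7.4.1), and BUN and creatinine are measured before each dose (7.4.5). Doses #2 and #3 are expected to be outpatient and are affected only if IV fluids are running.

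Most of this stands, and it keeps the point minor. It does not remove the point. Section 7.4.6 agrees with itself but not with 6.1.5.b, which makes 5% conditional. If 5% is meant to bind, 6.1.5.b is too loose; if 6.1.5.b governs, the stated volume and the cut are wrong for some permitted infusions. The protocol gives no reason for removing up to twice the infused volume at 10%. A clinician who adjusts sensibly has to depart from an instruction written as a fixed number.

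A reader might go further and infer that 7.4.6 contradicts 7.4.5, or that infants would become volume depleted. The documents support neither. Section 7.4.5 requires that the infant is not depleted before the infusion starts, and a cut on the infusion day is compatible with that. The protocol sets no daily fluid target, so the 10 mL/kg is a gap against the IV fluid ordered, not a measure of need or of volume status.

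**Conclusion.** The point holds as a minor flaw in a bedside instruction. The volume in 7.4.1 and 7.4.6, and the cut in 7.4.6, fit a 5% infusion only, while the protocol also permits 10%. At 10% the cut can exceed the infused volume by 0 to 10 mL/kg relative to the IV fluid ordered that day, depending on F. At 5% there is no excess for a full dose at any F.

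This rests on reading 6.1.5.b as a recommendation and not a requirement, and on the instruction being followed literally. The exposure is essentially one monitored inpatient day around dose #1, and feeds or clinical judgment may offset it.

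**What to change.** In 7.4.6, replace the fixed figure with a rule tied to concentration: reduce IV fluids by the planned IVIG volume at the concentration to be used (10 mL/kg at 10%, 20 mL/kg at 5%), with a larger cut allowed where the treating physician is concerned about overload. In 7.4.1 and 7.4.6, give the infusion volume as 10-20 mL/kg depending on concentration.

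The new sentence should not order fluid to be given back when an infusion stops early. Section 7.4.1 has infusions slowed or stopped at a systolic pressure of 112 mmHg or more, before the cause is settled, so such an order could return fluid to a hypertensive infant. Management after a stopped infusion should stay with the existing steps in 7.4.1 and with 7.4.6, under which, for fluid volume problems, "the infusion will be stopped and appropriate steps will be taken to reduce fluid intake".

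The cost is one sentence in 7.4.6 and one phrase in each of 7.4.1 and 7.4.6. It needs no extra patients, procedures, data fields or analyses. Local dilution policy is unchanged, and at 5% the cut stays at 20 mL/kg.
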